18.4 APPENDIX 4: TFEQ-R18V2¹⁷

The Three-Factor Eating Questionnaire

Please read each statement and select from the multiple-choice options the answer that indicates the frequency with which you find yourself feeling or experiencing what is being described in the statements below.

1. When I smell a delicious food, I find it very difficult to keep from eating, even if I have just finished a meal.
Definitely true (4) / mostly true (3) / mostly false (2) / definitely false (1)
2. I deliberately take small helpings as a means of controlling my weight.
Definitely true (4) / mostly true (3) / mostly false (2) / definitely false (1)
3. When I feel anxious, I find myself eating.
Definitely true (4) / mostly true (3) / mostly false (2) / definitely false (1)
4. Sometimes when I start eating, I just can't seem to stop.
Definitely true (4) / mostly true (3) / mostly false (2) / definitely false (1)
5. Being with someone who is eating often makes me hungry enough to eat also.
Definitely true (4) / mostly true (3) / mostly false (2) / definitely false (1)
6. When I feel blue, I often overeat.
Definitely true (4) / mostly true (3) / mostly false (2) / definitely false (1)
7. When I see a real delicacy, I often get so hungry that I have to eat right away.
Definitely true (4) / mostly true (3) / mostly false (2) / definitely false (1)
8. I get so hungry that my stomach often seems like a bottomless pit.
Definitely true (4) / mostly true (3) / mostly false (2) / definitely false (1)
9. I am always hungry so it is hard for me to stop eating before I finish the food on my plate.
Definitely true (4) / mostly true (3) / mostly false (2) / definitely false (1)
10. When I feel lonely, I console myself by eating.
Definitely true (4) / mostly true (3) / mostly false (2) / definitely false (1)
11. I consciously hold back at meals in order not to weight gain.
Definitely true (4) / mostly true (3) / mostly false (2) / definitely false (1)

12. I do not eat some foods because they make me fat.

Definitely true (4) / mostly true (3) / mostly false (2) / definitely false (1)

13. I am always hungry enough to eat at any time.

Definitely true (4) / mostly true (3) / mostly false (2) / definitely false (1)

14. How often do you feel hungry?

Only at meal times (1) / sometimes between meals (2) / often between meals (3) / almost always (4)

15. How frequently do you avoid “stocking up” on tempting foods?

Almost never (1) / seldom (2) / moderately likely (3) / almost always (4)

16. How likely are you to consciously eat less than you want?

Unlikely (1) / slightly likely (2) / moderately likely (3) / very likely (4)

17. Do you go on eating binges though you are not hungry?

Never (1) / rarely (2) / sometimes (3) / at least once a week (4)

18. On a scale of 1 to 8, where 1 means no restraint in eating (eating whatever you want, whenever you want it) and 8 means total restraint (constantly limiting food intake and never “giving in”), what number would you give yourself?

Revised 18-Item (Karlsson et. Al. 2000)

18.5 APPENDIX 5: VAS AND DAILY DIARY APPLICATION

Recommended primary scales for self-reported appetite in healthy adults^a

Scale	Question	Anchors	
		Low	High
Hunger	How hungry are you?	I am not hungry at all	Extremely I have never been more hungry
Fullness	How full are you?	I am completely empty	I cannot eat another bite

^aLine scales 100-150 mm (paper) or appropriate length for electronic capture systems are to be used for each of these questions.

ELIRA THERAPUTICS PROTOCOL CD-005

Subject Number _____ **Week** _____

Directions: Answer each question about how you are feeling, by drawing a mark (X) through the horizontal line of each question.

- | | | |
|--|---|--|
|  30 minutes before breakfast
 90 minutes after breakfast
 30 minutes before dinner |  30 minutes after breakfast
 Pre lunch
 bedtime |  60 minutes after breakfast
 Midafternoon |
|--|---|--|

Date: _____

Time: _____

Table 1	How Satisfied do you feel?	I have never been more hungry
I am not hungry at all	_____	
I am completely empty	_____	I cannot eat another bite
	How full do you feel?	
Not full at all	_____	Totally full
	How hungry do you feel?	
Nothing at all	_____	A lot
	How much do you think you can eat?	

Scoring: To be completed by study staff

Table One: 1- _____ 2- _____ 3- _____ 4- _____

Table Two: 1- _____ 2- _____ 3- _____ 4- _____

Table 2	Would you like to eat something sweet?	No, not at all
Yes, very much	_____	
	Would you like to eat something salty?	No, not at all
Yes, very much	_____	
	Would you like to eat something savory?	No, not at all
Yes, very much	_____	
	Would you like to eat something fatty?	No, not at all
Yes, very much	_____	

Subject initials and date _____

18.6 APPENDIX 6: SCHEDULE OF EVENTS

APPENDIX 6: SCHEDULE OF VISITS

STUDY PERIOD	SCREENING	ENROLLMENT	THERAPY/CONTROL						END OF STUDY ⁷
	VISIT 0	VISIT 1	VISIT 2	VISIT 3	VISIT 4	VISIT 5	VISIT 6	VISIT 7	VISIT 8
WEEK #	WEEK -1	WEEK 0	WEEK 1	WEEK 4	WEEK 8	WEEK 12	WEEK 16	WEEK 20	WEEK 24
VISIT WINDOW ¹	±7 DAYS	±7 DAYS	±7 DAYS	±7 DAYS	+/- 7 DAYS	+/- 7 DAYS	+/- 7 DAYS	±7 DAYS	±7 DAYS
Informed Consent	X								
Inclusion/Exclusion Criteria	X	X	X	X	X	X	X	X	X
Medical History	X								
Diet History	X								
Physical Exam	X								X
T6/T7 dermatome assessment	X ³	X ³	X ⁴	X ⁴	X ⁴	X ⁴	X ⁴	X ⁴	X ⁴
Blood Pressure	X	X	X	X	X	X	X	X	X
Height	X								
Weight	X	X	X	X	X	X	X	X	X
Laboratory Requisition - Blood Tests ²	X					X			X
Urine Pregnancy Test (FOCBP)	X	X ⁶							X
Administration of PHQ-9	X								X

Protocol #: CD-005; Version #: 4.0

Original Date: May 8, 2018 Revision Date: May 3, 2019

-Confidential-

Administration of TFEQ-R18V2		X	X	X	X	X	X	X	X
Administration of Pre-Study Survey	X								
Administration of Post-Study Survey									X
Provide/Train on Paper Diaries ³	X	X		X	X	X	X	X	
Collect and Review Paper Diaries ³			X	X	X	X	X	X	X
Randomization ⁵		X							
Provide/Train on Electronic Scale		X							
Provide and Train on Electronic Diary Application ⁴		X	X	X	X	X	X	X	
Collect and Review Electronic Diary ⁴			X	X	X	X	X	X	X
Provide and Train on TENS Unit and Patches ⁴		X	X	X	X	X	X	X	
Collect and Examine TENS Unit and Patches ⁴			X	X	X	X	X	X	X
Training on Electrode Placement ⁴		X	X	X	X	X	X	X	
Adjust TENS Unit, if applicable ⁴		X	X	X	X	X	X	X	
Provide/instruct (as needed) on TENS Clean-Cote Skin Wipes an/or Alcohol Prep Pads ⁴		X	X	X	X	X	X	X	
Provide/Instruct (as needed) on Cetaphil Lotion ⁴		X	X	X	X	X	X	X	
Concomitant Medication Review ³	X	X	X	X	X	X	X	X	X
Assessment of Adverse Events ³	X	X	X	X	X	X	X	X	X
Assessment of Adverse Device Effects ⁴		X	X	X	X	X	X	X	X
Schedule next visit	X	X	X	X	X	X	X	X	
Photographs taken		X				X			X
Study Exit									X

1 – all visits are ± 1 week

2 – Blood tests include HbA1c, lipid panel,

3 – to be completed for control and treatment group

4 – to be completed for treatment group only

5 – randomization into control or treatment group

[figure not shown]
6- Either Screening or Randomization Visit, Not Needed at Both.

Protocol #: CD-005; Version #: 4.0

Original Date: May 8, 2018 Revision Date: May 3, 2019

-Confidential-

18.7 APPENDIX 77: ELECTRONIC DIARY APPLICATION (SEE SAMPLES SCREEN SHOTS)

18.8 APPENDIX 8: LIST OF POTENTIAL DRUG INTERACTIONS

	Weight positive medications (cause weight gain)	Weight negative medications (cause no gain* or weight loss)
DIABETES	Glipizide Glyburide Insulin Pioglitazone Rosiglitazone	Acarbose* Exanatide Glimepiride* Liraglutide Metformin Sitagliptan*
HYPERTENSION	Atenolol Clonidine Hydralazine Labetalol Prazosin Terazosin Valsartan	Amlodipine Captopril* Carvedilol* Enalapril* Furosemide Hydrochlorothiazide* Lisinopril Losartan* Metoprolol* Olmesartan
PSYCHIATRIC	Citalopram Clozapine Lithium MAO-I Mirtazapine Olanzapine Paroxetine Phenothiazines Risperdone TCA	Amphetamines Bupropion Escitalopram* Fluoxetine Sertraline
CHRONIC PAIN	Amitriptyline Celecoxib Gabapentin Methadone Pregabalin	Acetaminophen* Baclofen* Carisoprodol* Cyclobenzaprine* Diclofenac* Fentanyl Hydromorphone Ibuprofen* Morphine Naproxen* Tramadol

FIGURE 1: Commonly prescribed weight positive, negative, and neutral* medications.

*List of drugs includes drugs that may impact study participation. May not be complete and is up to PI discretion.

18.9 APPENDIX 9: END OF STUDY SURVEY

Name or Subject Identifier: _____

ELIRA End of Study Survey

Thank you for completing the weight loss study. Please circle your response to each question below.

1. My experience wearing the device and using the associated app can be described as (enter text below):

2. What I liked MOST about this product (circle all that apply):

- Non-invasive / non-surgical
- Helps control appetite
- Easy to use
- Technology / app component
- Convenience / automatic nature
- No medications or pills
- Wearable
- Low side effects
- Discreet
- FDA cleared
- Other (please specify): _____

3. What I liked LEAST about this product (circle all that apply):

- Safety
- Side effects
- Efficacy (Effectiveness)
- Sensation while wearing it
- Skin patch / wearable
- Having to connect to a smartphone
- Not natural or healthy way to lose weight
- Other (please specify): _____

4. Overall, this product helped suppress my appetite (circle one):

- Always
- Most of the time
- Occasionally
- Never

Protocol #: CD-005; Version #: 4.0

Original Date: May 8, 2018 Revision Date: May 3, 2019

-Confidential-

5. I found that the instant sessions helped suppress my appetite (check one):
- Always
 - Most of the time
 - Occasionally
 - Never

6. Please indicate your level of agreement with the following statements (check one box for each statement):

	Strongly disagree	Somewhat disagree	Neutral	Somewhat agree	Strongly agree
The product easily fits my daily lifestyle.					
Wearing this product was comfortable					
I got used to using this product quickly.					
The app was easy to use					
The device seems safe.					
My appetite was lower than normal while using this product.					
The product helped me lose more weight than I could have on my own.					
I am happier with how I look and feel after wearing this product.					
I wish I could continue wearing this product.					
I believe this product would work for most people.					
I would recommend this product to my friends.					

7. Where would you expect that patients could purchase the Elira device? Circle all that apply.
- From my aesthetic physician (dermatologist, plastic surgeon, medspa)
 - From my general practioner or internal medicine physician
 - From my OB/GYN
 - From a weight lost clinic
 - Other (please specify): _____

7. What barriers to your normal lifestyle did using this product create:

8. I wish the following additions/changes could be made to the device:

9. I wish the following additions/changes could be made to the Smartphone application:

10. I would pay this much money out-of-pocket for this device: _____

11. I am willing to be contacted by Elira for more details on my experience after this trial to help improve the product design:

- YES
- NO

12. I am willing to allow Elira to use this information as a user testimonial (using my first name only):

- YES
- NO

18.10 APPENDIX 10: PRE-STUDY SURVEY

Name or Subject Identifier: _____

ELIRA Pre-Study Survey

Thank you for your interest in the weight loss study. Please circle your response to each question below.

1. How much weight do you think you need to lose?
 - a. None
 - b. Less than 5 lbs
 - c. 5 – 10 lbs
 - d. 11 – 15 lbs
 - e. 16 – 20 lbs
 - f. More than 20 lbs
 - g. Not sure

2. A number of weight loss programs offer the potential to lose 1-2 lbs per week. Do you consider this a reasonable amount of weight for you to lose per week in a weight loss program?
 - a. Yes
 - b. No, I would expect to lose less than 1 pound per week
 - c. No, I would expect to lose more than 2 pounds per week

3. Which, if any, of the following have you attempted in order to lose weight in the past? Select all that apply.
 - a. Dieting on your own (not through a specific program)
 - b. Dieting with free online coaching or support (like MyFitnessPal)
 - c. Exercise or increasing amount of exercise
 - d. Paid weight loss program (Jenny Craig / Weight Watchers, etc.)
 - e. Gym membership
 - f. Medical weight loss through a physician
 - g. Prescription diet pills or other prescription medications
 - h. Over-the-counter diet pills or appetite suppressants
 - i. Surgical or other invasive procedures, e.g. gastric balloons or LAP-band
 - j. Body sculpting targeting specific areas, e.g. Cool Sculpting
 - k. Other (please specify)
 - l. I haven't tried to lose weight in the past

4. How would you describe your level of success with prior weight loss methods?
 - a. I was able to lose weight and keep all or most of the weight off
 - b. I was able to lose weight but regained some or most of the weight back
 - c. I was not able to lose weight

5. What is the primary reason you want to lose weight? Please circle one.
 - a. Better health
 - b. Improved appearance
 - c. Lifestyle (e.g. being more active)
 - d. Recommended by my Company's wellness program
 - e. Special event (wedding, reunion, party, etc.)

Protocol #: CD-005; Version #: 4.0

Original Date: May 8, 2018 Revision Date: May 3, 2019

-Confidential-

f. Other (please specify) _____

- 6. Is it easy or difficult for you to lose weight?
 - a. Very easy
 - b. Somewhat easy
 - c. Sometimes easy, sometimes difficult
 - d. Somewhat difficult
 - e. Very difficult
 - f. I've never tried to lose weight before

- 7. What are your primary barriers to weight loss? Select all that apply.
 - a. Time
 - b. Cost
 - c. Willpower
 - d. Appetite control
 - e. Fear of failure
 - f. Concerns about side effects of medication or surgery
 - g. Other (please specify)

8. Please indicate your level of agreement with the following statements

	Strongly disagree	Somewhat disagree	Neutral	Somewhat agree	Strongly agree
I always try to look and feel my best					
I try to keep up with the latest trends					
How you look on the outside says a lot about you					
I enjoy shopping for new clothes					
I would be more confident if I lost weight					
I feel like I'm hungry more often than other people					
Hunger is my biggest barrier to losing weight when dieting.					
I have talked to a friend or family member about trying to lose weight					
I have been frustrated by my weight for a long time					
I wish I could control how much I eat					
I wish I could lose weight without exercising					
Losing weight is a very difficult process					
Posiitve messages motivate me to stay on track with my goals.					

18.11 APPENDIX 11: DIET GUIDELINES

The Centers for Disease Control and Prevention has information available online that you may want to reference. Some helpful information and links are below:

“Whether you need to lose weight, maintain your ideal weight, or gain weight, the main message is – calories count! Weight management is all about balancing the number of calories you take in with the number your body uses or “burns off.”

If you need to lose weight, you’ll need to reduce your daily calorie consumption in line with your goal. An adult can lose 1 to 2 pounds per week by eating 500-1,000 fewer calories per day. During this study, try to reduce your calorie intake as much as possible.”

Links to specific pages on the CDC website are below:

Losing Weight: https://www.cdc.gov/healthyweight/losing_weight/index.html

Healthy Eating: https://www.cdc.gov/healthyweight/healthy_eating/index.html

Cutting Calories: https://www.cdc.gov/healthyweight/healthy_eating/cutting_calories.html

Meal Ideas: https://www.cdc.gov/healthyweight/healthy_eating/cutting_calories.html

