Study Design	
Randomized, adaptive parallel arm study. Subjects will be initially screened during a screening period (+/- 7 days). During this screening period, subjects will sign an Informed Consent Form (ICF), have their weight/height and blood pressure measured as part of a physical exam, take a pregnancy test (females of child bearing potential), get blood drawn for analysis (blood lipids, HbA1c), and complete the PHQ-9 and pre-study survey. Subjects will be asked to complete their first batch of diaries to set a baseline hunger value.
 
At the end of the screening period, eligible subjects will be enrolled/randomized in the study and be randomized to either a treatment or control group. After enrolling, both control and treatment subjects will be instructed to follow a healthy diet and reduce calories as desired for the duration of the study and will receive training on the use of the electronic scale and completion of paper diaries. For the treatment group, subjects will be instructed on use of the Elira wearable patch system. Photographs will be taken at the enrollment visit. Following this, subjects will enter the Therapy Period for ~24-weeks.
 
At the 12 week visit, subjects will be assessed for weight loss, blood pressure, blood lipids, HbA1c, patient preference questionnaire and their participation will continue through months 4-6 for the Safety phase of the Therapy Period. The Therapy Period will be considered complete (pending laboratory results, adverse events or serious adverse events). Patient (treatment) photographs will also be taken at the 12 week visit.

Protocol #: CD-005; Version #: 4.0

Original Date: May 8, 2018 Revision Date: May 3, 2019

-Confidential-

	
The study utilizes an adaptive approach where cohorts of enrolled/randomized subjects (in groups of ~25 per arm) are assessed for dose response and progression to achievement of primary and secondary endpoints. Frequent interim endpoint assessment utilizing Markov-chain Monte Carlo (MCMC) methods coupled with Longitudinal analyses will be utilized to determine sample sizes for future cohorts (assessed primarily via Normal dynamic linear modeling [NDLM]). Long term safety of the device will be shown through 6 months of usage.

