8.2 Justification of Sample Size

As per the protocol, the calculation sample size for the study is based on conservative imputation of results from other studies on weight loss including the use of TENS for weight loss. The degree of coaching/dietary support throughout the present study is moderate intensity lifestyle/weight coaching. The sample size modeling assumes an average of 3.5% TBWL in Control Subjects using diet and exercise alone. The estimated weight loss in Treatment Subjects is modeled from preliminary data on T6/T7 dermatomal TENS when used for

weight loss: 6% TBWL. The variance of the responses in the study (i.e. Standard Deviation) was modeled at +/- 5% TBWL. This value was taken from previous dermatomal TENS weight loss study results. The model assumes a 30% drop out rate across groups and an 80% powered endpoint using an adaptive p spending model wherein interim posterior probability assessments are allowed after enrolling proscribe cohorts of not less than 67% of subjects. The alpha penalty will be minimized per interim by assessing the relationship between stimulation (i.e. dose) and weight loss using Normalized Linear Dynamic Modeling (NLDM) to determine overall sample size projected (i.e. futility) rather than assessing the primary hypothesis per se. Monotonicity will not be assumed in this analysis. This modeling provides an estimate of 80 subjects per group, for a total study size of 160 subjects. However, the protocol allows for enrollment of additional subjects should the interim model project under powering of the primary endpoint.

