9.10 DIET

Subjects will be encouraged to maintain a healthy lowcalorie diet throughout the study. The study doctor and/or research coordinator will provide guidance to assist the subjects on maintaining the diet.

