9.11 ELECTRONIC DAILY DIARY DEVICE

For Treatment Group Subjects only, an Android Smart Phone running a semi-custom daily diary application to capture hunger, calories, and weight will be provided. Subjects will be instructed on use by PI or designee.

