10.1.2 Risks associated with appetite loss

While appetite loss is beneficial to weight loss, severe appetite suppression may place the subject at risk for hypoglycemia and dehydration which may entail risks to alertness and other conditions. Prolonged appetite suppression can cause alterations in mood and mental acuity and impact activities of daily living (ADL).

Adverse Events: The adverse events listed below are anticipated to occur at low frequency, and the subject needs to be aware that they may occur.

From TENS:

Paresthesia

Burning sensation

Pain

Skin irritation (urticaria) at or near the electrode application site

Protocol #: CD-005; Version #: 4.0

Original Date: May 8, 2018 Revision Date: May 3, 2019

-Confidential-

Redness at site of stimulation
Mild swelling at site of electrode stimulation
Nausea
GI discomfort
Dyspepsia
Heartburn
Cramping
Gastroparesis

From appetite loss:

Mild hypoglycemia
Dehydration
Alterations in mood
Mild trouble sleeping
Alterations in mental acuity
Anorexia

From potential use of anti-nausea medication (PI Discretion):

Drowsiness
Dizziness
Constipation
Stomach upset
Blurred vision
Dry mouth/nose/throat may occur
Mental/mood changes (such as restlessness, confusion)
Difficulty urinating
Fast/irregular heartbeat

From potential use of Cetaphil Moisturizing Lotion

Irritation
Swelling

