11. ADVERSE EVENTS: DEFINITIONS & REQUIREMENTS

At each evaluation, the Investigator will determine whether any adverse events (AEs) have occurred. For the purpose of this Protocol, an AE is any undesirable clinical occurrence in a subject whether or not related to the investigational treatment. Any pre-existing condition that exhibits a change in nature, severity or degree of incidence during the clinical study is an AE. This definition does not depend on a causal relationship with the device or the Protocol requirements. AEs will be tracked and categorized as outlined within the present protocol.

Subjects are encouraged to report AEs with or without questioning (e.g., How has your health been since the last visit?). If it is determined that an AE has occurred, the Investigator will obtain all the information required to complete the AE Case Report Form.

In addition, subjects will be instructed to contact the Investigator and/or designee if any significant AEs occur between study evaluation visits. Serious AEs and unanticipated adverse device effects will be collected throughout the entire course of the study.

The Investigator will use the following definitions to assess the relationship of the AE to the use of the TENS system and/or daily electronic diary:

Not Related	
 ▪ Not associated with device application ▪ Due to an underlying or concurrent illness or effect of another device or drug
Unlikely	
 ▪ Little or no temporal relationship to the study device and/or ▪ A more likely alternative etiology exists
Possible	
 ▪ Temporal sequence between device application and event is such that the relationship is not unlikely or ▪ Subject's condition or concomitant therapy could have caused the AE
Probable	
 ▪ Temporal sequence is relevant or ▪ Event abates upon device application completion/removal or ▪ Event cannot be reasonably explained by the subject's condition
Highly Probably	
 ▪ Temporal sequence is relevant and ▪ Event abates upon device application completion/removal or event recurs on repeated device application

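### The diet sheet given to both arms urges the largest calorie cut achievable, against the protocol summary's wording that leaves the amount to the subject; replace that sentence (minor safety and consistency point)

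*Combined protocol and SAP*

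**What the plan says.** Appendix 11 (numbered 18.11) is the diet sheet. The Visit Schedule in the protocol summary and the table in section 9 both have it handed to treatment and control subjects at the randomization visit. Its text sits inside quotation marks and is introduced as information from a public health agency. It first advises a reduction matched to the subject's goal, then states "An adult can lose 1 to 2 pounds per week by eating 500-1,000 fewer calories per day", and then ends, still inside the quotation, with "During this study, try to reduce your calorie intake as much as possible".

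The Study Design row of the protocol summary says that subjects in both arms will be "instructed to follow a healthy diet and reduce calories as desired for the duration of the study". The Visit Schedule asks for a calorie reduction if the subject can manage one. Sections 9 and 9.10 encourage a healthy, low-calorie diet without a number, and 9.10 adds "The study doctor and/or research coordinator will provide guidance to assist the subjects on maintaining the diet".

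On risk, section 10.1.2 states that "severe appetite suppression may place the subject at risk for hypoglycemia and dehydration".

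On expected weight loss, section 8.2 states "The sample size modeling assumes an average of 3.5% TBWL in Control Subjects using diet and exercise alone". It sets 6% for treatment, with a standard deviation of 5%.

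**The concern.** The same subjects receive two different instructions. The protocol summary leaves the amount to them; the sheet they take home asks them to try for as large a cut as they can. The sheet also goes further than its own preceding advice. Because the sentence stands inside the agency quotation, a subject may take it for public health advice, although it speaks of this study.

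What is at stake is a small, avoidable safety exposure. It falls mainly on device subjects, whose appetite is being suppressed while they are urged in writing to restrict further. No section available for review states a maximum cut or a minimum daily intake.

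**Working it through.** The plan states no figure on this point, so there is none to reproduce. Two checks apply.

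**1. The wording side by side**

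| Place | Who receives it | Size of the cut |
|---|---|---|
| Protocol summary, Study Design | Both arms | Left to the subject |
| Protocol summary, Visit Schedule | Both arms | If the subject can manage one; no amount |
| Sections 9 and 9.10 | Both arms | Low-calorie diet; no amount; staff guidance |
| Appendix 11, middle lines | Both arms | Matched to goal; 500 to 1,000 per day described |
| Appendix 11, last text sentence | Both arms | As large as the subject can achieve |

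Only the last row asks for the largest achievable cut.

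**2. Does the trial need that sentence to reach its planned losses?**

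Inputs:
- Mean losses of 3.5% (control) and 6% (treatment), from section 8.2. They are taken over 12 weeks because the co-primary weight endpoint is at 3 months.
- The sheet's conversion: 500 fewer calories per day for each pound lost per week.
- Body weights from the eligible BMI range (25 to 35) and the height range in Appendix 1. At 152.4 cm and BMI 25: 25 × 1.524² = 58.1 kg, about 128 lb. At 193.0 cm and BMI 35: 35 × 1.930² = 130.4 kg, about 287 lb.

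Formula: average daily cut = weight (lb) × proportion lost ÷ 12 × 500.

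| Weight | 3.5% loss | 6% loss |
|---|---|---|
| 128 lb | 187 | 320 |
| 155 lb | 226 | 388 |
| 215 lb | 314 | 538 |
| 287 lb | 419 | 717 |

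For example, 287 × 0.06 ÷ 12 × 500 = 717 calories per day. Every figure lies below the top of the sheet's 500 to 1,000 range, and the control figures lie below its bottom. The calculation credits all weight loss to diet; any loss from exercise would lower the cuts needed. These are averages for the planned means, not limits for individuals.

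**The case against.** The strongest reply is that the sentence is over-read. It says only to try, and it follows directly on advice tied to the subject's goal and a stated range, so it can be taken as encouragement within that advice. The protocol summary sets no upper limit either. There are also real safeguards:
- Diagnosed eating disorders and HbA1c above 6.5 are excluded (section 7.2).
- Weight, blood pressure and adverse events are checked at every therapy visit in both arms (Appendix 6).
- Unscheduled safety visits and approved dose reduction are allowed (section 5.1).
- All subjects keep a paper diary that includes weight and diet (section 5.2).
- Treatment subjects have a "semi-custom daily diary application to capture hunger, calories, and weight will be provided" (section 9.11).
- Between visits, "subjects will be instructed to contact the Investigator and/or designee if any significant AEs occur between study evaluation visits" (section 11).

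Much of this stands, and it keeps the point minor. But the milder reading is not the only natural one. The safeguards detect or respond to trouble; none corrects the sheet the subject takes home.

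Three stronger readings are tempting, and the documents do not support them.

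*That 1,000 calories per day is a safe ceiling which the sheet should print.* The sheet gives 1,000 as the top of a description of ordinary weight loss, not as a safety limit. One absolute figure would cover subjects from about 128 to 287 lb, with no floor. If usual intake were 1,700 to 2,000 calories (an assumption; the documents give none), such a cap would still permit 700 to 1,000 per day. Nor would it be free. It equals 24 lb in 12 weeks, which is 11.2% of 215 lb and 8.4% of 287 lb. With normally distributed losses at the section 8.2 means and standard deviation, all from diet, 15.1% of device subjects and 6.3% of controls at 215 lb would exceed it. At 287 lb the shares are 31.8% and 16.5%, and truncating losses there would take 0.59 points off the planned 2.5-point difference.

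*That harm is shown.* Section 10.1.2 links hypoglycemia and dehydration to severe appetite suppression, not to voluntary dieting. It lists mild hypoglycemia among events expected at low frequency. That maximal restriction would add to the risk is a clinical judgement, and the documents give no rate.

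*That the sentence biases the comparison.* Both arms receive the same sheet, so nothing in the wording favours one arm.

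**Conclusion.** The inconsistency is real and the concern holds as a minor safety and consistency point. A handout for both arms contains an open-ended instruction to restrict calories that conflicts with the protocol summary and exceeds the sheet's own advice, in a trial that already names risks of severe appetite suppression. The planned mean losses correspond to average cuts of about 187 to 717 calories per day, so the sample size assumptions do not depend on the sentence. That range rests on the sheet's own conversion, a 12-week period, weight loss from diet alone, and body weights at the extremes of Appendix 1. The size of any safety benefit cannot be given from the documents, and no change in power is claimed.

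**What to change.** Delete the last text sentence of Appendix 11 and print in its place, outside the agency quotation, wording drawn from the protocol summary:

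*During this study, follow a healthy diet and reduce calories as desired; talk to the study doctor before making large cuts.*

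Leave to the clinical lead whether to add a maximum daily cut or a minimum daily intake, and at what level. The protocol summary, the Visit Schedule and section 9.10 need no change, since none of them asks for a maximal cut.

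The cost is one sentence in a subject handout, handled as an amendment that needs written IRB approval before use (section 13.1). It requires no extra subjects, visits or data. Subjects who would have restricted most may lose slightly less weight.
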